## **Project Summary**

The aim of this Pilot study is to determine whether robotically targeted lower-limb pedaling therapy can increase the extent of stroke recovery on behavioral measures and induce brain plasticity as measured by functional magnetic resonance imaging (fMRI). Forty (40) adult stroke patients and 80 healthy controls will be enrolled in this study. Of the 40 patients, half will be randomly assigned to the robotically-targeted training ("robotic") group and will receive training on the targeted training task. The other half of the patients will perform a duration-matched aerobic pedaling exercise ("control" group). All stroke patients will be scanned before and after their training program while performing or imagining simple motor tasks. Behavioral assessments of motor and cognitive capacities will be collected at each timepoint. Healthy control subjects enrolled for device testing (20) will receive up to 5 training sessions in a modified robotic paradigm and 1 fMRI scan, in order to investigate motor learning and brain activity in a novel motor control task. Additional healthy pilot subjects (up to 60) will test training protocols and assessments during preparatory design phases of the project.

## **Background and Significance**

Previous studies have shown that robotic therapy can enhance functional and motor recovery in stroke survivors. The best results are from upper-limb therapies designed to incentivize volitional muscle control on the part of the patient, usually in robotically-perturbed reaching tasks. Lower-limb robotic therapies have focused primarily on using robotic exoskeletons to assist motion of the legs during walking, an approach that has been criticized for not requiring volitional control from the patient. Here we plan to adapt the robotically-targeted control incentivization common in upper-limb therapy to a lower-limb pedaling task. A robotic exercise cycle will reward improved activation or control of impaired neural motor circuits, by varying the controlled speed or resistance of the cycle in response to user performance. The patient's task will be to produce pedal forces in specific directions, or electromyographic signals (EMG) in particular patterns, designed to elicit activity in impaired motor circuits of the brain. We will combine this robotic therapy with behavioral measures of leg function, kinematic measures of leg function during walking, and functional magnetic resonance imaging (fMRI) to determine if the targeted therapy can improve stroke recovery to a greater extent than a simple pedaling exercise. Unlike many previous approaches, the pedaling task could ultimately be used in early- stage recovery, before patients are able to walk. Also, it specifically targets and rewards improvements in volitional control of impaired motor circuits, instead of functional outcomes that may reward compensation rather than true motor recovery.

## **Specific Aims**

To evaluate motor recovery following a targeted robotic training regimen, in comparison to aerobic cycling, in stroke patients with chronic impairment of moderate severity.

To determine if this therapy induces greater brain plasticity in comparison to aerobic pedaling exercise, as measured by functional magnetic resonance imaging (fMRI).

## **Study Objectives**

### ***Primary objective***

To examine the effect of a robotic pedaling therapy program that rewards coordinated foot pedal forces and EMG patterns on lower-limb function during pedaling and walking, in comparison to an aerobic pedaling task.

### ***Secondary objective***

To examine plasticity changes as measured by fMRI measures before and after robotic pedaling therapy, in comparison to an aerobic pedaling task.

## **Study Outcomes**

### ***Primary outcome***

The primary outcome is behavioral gait function, as measured from the Six Minute Walk Test (6MWT), self-selected walking speed (SSWS) and fastest comfortable walking speed (FCWS). Measures of interest will include speed, distance walked, and variability, symmetry and stability of foot placement patterns, as measured by foot-worn inertial motion sensors.

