### **Data Processing/Data Analysis**

#### ***Behavioral Data:***

For the analysis of pre- and post- measures on the behavioral data, we will perform repeated measures ANOVA tests with time as the independent variable and score on

each behavioral test as the dependent variable.

In order to assess the overall effect of the rehabilitation protocol, we will perform multiple regression analyses to determine the extent to which data from each modality explains the proportion of the variance in the behavioral outcomes. The dependent variable is the score on the behavioral test and the predictors are the task tracking performance (error) in EMG and foot force during the last training session, and the percent signal change in targeted brain areas from the fMRI data.

In addition, we will also perform a multivariate ANOVA to examine the mixed model with Time of testing (pre, post) as a within subject factor, Group (robotic therapy, aerobic therapy) as the between-subject factor, and dependent variables of percent signal change from the fMRI data and each of the behavioral scores. This will help us to determine if there is a significant difference between the groups in terms of behavioral performance and functional activations and also to determine whether these dependent measures change over time.

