***fMRI data:***

SPM5 (Wellcome Department of Cognitive Neurology, London, UK) will be employed for motion correction and used to normalize the EPI BOLD images to a standard space using a 12 parameter linear transformation. The images will be then spatially smoothed using an 8.0 mm Gaussian kernel. Finally, the statistical package contained within SPM5 will be used to estimate the effects of condition at each voxel according to the general linear model. The analysis will be entered into SPM5 as an epoch design of the fixed response/box car form convolved with canonical HRF, reflecting the appropriate activation and rest periods within the total scanning period. Images will be high-pass filtered at 128 s to remove low- frequency drifts in blood oxygen level-dependent signal.

Percent signal change (after vs. before) will be compared statistically between the two groups using unpaired two-sample t-tests between the robotic and aerobic groups. A repeated measures ANOVA will be performed with the dependent variable being the percent signal change and between subjects factor Group (robotic therapy, aerobic therapy), and within subject factor Time (before and after training).

Along with percent signal change over time, we will also compute region-wise laterality index. ROIs will be predefined in each hemisphere. For each ROI, laterality index (LI) will be defined as: Number of activated voxels in the affected hemisphere / [voxels in the left hemisphere + voxels in the right], thus giving LI for each ROI. LI = 0.5 indicates symmetrical activation; LI < 0.5 indicates an activation deficit on the affected side, and LI > 0.5 indicates increased activation of the affected side. This index will provide a way of

understanding the contribution of each brain area (ROI) to the overall task-related activation in one session and changes in laterality over time. The percent signal change and LI are purely quantitative measures, in order to ensure that change in plasticity over time is captured adequately and does not rely on individual fMRI reader's abilities to gauge these changes simply on the basis of a "visual read" of the fMRI scans.

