fMRI data is in the form of many voxels that are traditionally analyzed separately. This analysis needs to be corrected for the thousands of statistical tests performed. Corrections need to consider the spatial nature of fMRI data so simple schemes, such as the Bonferroni correction, are not appropriate. A method that controls the family-wise error (FWE) balances the statistical threshold with a minimum cluster size to produce an overall p-value for an activation cluster (Forman et al. 1995). We will use this FWE technique to correct our functional data for multiple comparisons.

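### The primary objective compares the two arms on walking, but the plan names no gait-specific between-arm test and no lead walking test

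*Combined protocol and SAP*

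**What the plan says.** The Primary objective section asks for the effect of robotic pedaling "on lower-limb function during pedaling and walking, in comparison to an aerobic pedaling task". This is a between-arm question.

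The Primary outcome section gives three walking tests: "The primary outcome is behavioral gait function, as measured from the Six Minute Walk Test (6MWT), self-selected walking speed (SSWS", with FCWS completing the list. It continues: "Measures of interest will include speed, distance walked, and variability, symmetry and stability of foot placement patterns". It gives no ranking, composite or rule for calling the outcome positive.

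The Behavioral Data section plans three analyses:

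- For each behavioral score, "we will perform repeated measures ANOVA tests with time as the independent variable".
- A multiple regression of the behavioral score on last-session tracking error and fMRI signal change.
- A multivariate ANOVA with Time within subjects and Group between subjects, with "dependent variables of percent signal change from the fMRI data and each of the behavioral scores". Its stated purpose is "to determine if there is a significant difference between the groups in terms of behavioral performance and functional activations".

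For the secondary fMRI outcome, percent signal change "will be compared statistically between the two groups using unpaired two-sample t-tests between the robotic and aerobic groups", and a repeated measures ANOVA with Group and Time follows. The only multiplicity statement is also in the fMRI section: "We will use this FWE technique to correct our functional data for multiple comparisons".

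The Sample Size section sizes each walking test separately at alpha 0.05 and 80% power. It then chooses 16 evaluable patients per arm, the one-tailed figure for the 6MWT.

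**The concern.** A time-only ANOVA shows whether patients changed from before to after training. Both arms train for the same number of sessions and both may improve, so a significant time effect says nothing about whether robotic training beats aerobic pedaling. If the analysis section is followed as written, the one test of walking that involves group is an omnibus test shared with brain activation and all the other behavioral scores. The primary question could end without a direct answer, while the secondary fMRI question has one.

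The missing lead test adds to this. With three tests, further sensor-based measures of unstated rank and no success rule, the walking result that counts could be chosen after the data are seen.

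**Working it through.** **1. The plan's own sample sizes.** Inputs are from the Sample Size section: 6MWT 154.3 (SD 171.1) m, SSWS 0.21 (SD 0.13) m/s, FCWS 0.18 (SD 0.15) m/s; z = 1.96 two-tailed or 1.65 one-tailed, plus 0.84. Formula: N per group = 2 × ((z + 0.84) × SD / d)².

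| Test | Two-tailed | Stated | One-tailed | Stated |
|---|---|---|---|---|
| 6MWT | 2 × (2.80 × 171.1/154.3)² = 19.3 | 20 | 2 × (2.49 × 171.1/154.3)² = 15.2 | 16 |
| SSWS | 2 × (2.80 × 0.13/0.21)² = 6.01 | 6 | 2 × (2.49 × 0.13/0.21)² = 4.8 | 5 |
| FCWS | 2 × (2.80 × 0.15/0.18)² = 10.9 | 11 | 2 × (2.49 × 0.15/0.18)² = 8.6 | 9 |

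With 20% dropout, 16/0.80 = 20 per arm. The figures reproduce (6.01 strictly rounds up to 7, which is immaterial). Each test uses the whole alpha of 0.05.

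**2. Which planned analysis compares the arms on which outcome.**

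| Analysis | Group term? | Specific to gait? |
|---|---|---|
| Per-score repeated measures ANOVA | No | Yes, per test |
| Multiple regression | No | Yes, per test |
| Multivariate ANOVA | Yes | No: fMRI signal change and every behavioral score are included |
| fMRI two-sample t-test | Yes | No: fMRI only |
| fMRI Group and Time ANOVA | Yes | No: fMRI only |

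No row has both a group term and a gait-specific outcome. This step needs no assumption.

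**3. False-positive chance if any one of three two-sided 0.05 tests counted.** The documents give no correlation between the tests, so a range is shown. At zero correlation it is 1 − 0.95³ = 14.3%. For a common correlation r it is 1 − ∫ φ(x) [Φ((1.96 − √r·x)/√(1−r)) − Φ((−1.96 − √r·x)/√(1−r))]³ dx, which gives 12.5% at 0.5, 10.9% at 0.7, 9.8% at 0.8 and 8.4% at 0.9. Simulated two-sample t-tests with 16 per arm agree: 11.1% at 0.7 and 8.5% at 0.9. With SSWS and FCWS correlated at 0.9, and 6MWT at 0.7 with each, the result is 10.0%. Holm at correlation 0.7 gives 4.0%.

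**4. Power of each test alone at 16 per arm.** Noncentral t with 30 degrees of freedom and noncentrality (d/SD) × √(16/2):

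- 6MWT: 0.902 × 2.828 = 2.55, power 69% two-sided (80% one-sided).
- SSWS: 1.615 × 2.828 = 4.57, power 99% two-sided.
- FCWS: 1.20 × 2.828 = 3.39, power 91% two-sided.

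**5. Cost of Holm.** Holm yields at least one success when the smallest p-value is below 0.05/3. Simulated at correlation 0.7, two-sided, the chance of at least one success goes from 99% unadjusted to 98% at the stated effects. Those effects are defined as post- versus pre-training differences, so between-arm effects may be smaller. If they were half as large (an assumption), the chance falls from about 66% to about 46%. At correlations of 0.5 and 0.9 the corresponding falls are 70% to 50% and 61% to 42%.

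**The case against.** The strongest reply is that the multivariate ANOVA already contains Group and Time for the walking scores and is meant to detect group differences in behavior. As a single omnibus test it can control error for its own global null, and the wording may allow results to be read variable by variable. A reader might infer that the plan never compares the arms on gait at all; the documents do not support that. What remains is narrower: no gait-specific follow-up is stated, Group by Time is not named as the test of interest, and a significant omnibus result could come from fMRI or a non-gait score.

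A reader might also infer that the trial runs at an 11% false-positive rate. That is not supported either. The any-one-test rule appears nowhere in the documents, and the correlation is assumed.

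The pilot purpose also carries weight. The Sample Size section says it wants to capture many metrics, so several measures were intended, and strict familywise control is partly a matter of choice. This lowers the stakes. It does not remove the need for a direct arm comparison: the Project Summary aims to determine whether the therapy can increase recovery, the Behavioral Data section looks for a significant group difference, and the Sample Size section sets alpha and power.

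**Conclusion.** The point holds in its main part without any assumption: the plan states no gait-specific between-arm test for a primary objective that is a between-arm comparison on walking, although it states two such tests for the secondary fMRI signal change.

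The absence of a lead test or success rule is a real but secondary gap. Its size, about 8% to 14% (10% to 11% near correlation 0.7), depends on an any-one-test rule that the plan neither states nor excludes, and on assumed correlations. The sensor-based foot-placement measures are not counted in that figure. This should be corrected before outcome data are analysed; in a pilot it is not a fatal flaw.

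**What to change.** In the Behavioral Data section, make the primary analysis the between-arm comparison of change (Group by Time) for each of 6MWT, SSWS and FCWS, using the model already planned for fMRI signal change. Report all three estimates with confidence intervals. Fix one- or two-sided testing in advance, since the Sample Size section computes both. Describe the time-only ANOVAs and the multivariate ANOVA as supportive.

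Before outcome data are analysed, either name one lead walking test, with the other two secondary, or apply Holm across the three at overall 0.05. Make the foot-placement measures secondary. The choice of lead test belongs to the investigators, and the documents point both ways: the Sample Size section sets 16 per arm on a one-tailed 6MWT test but also treats the 6MWT as an outlier among the sample size estimates. The 6MWT has the lowest power of the three at the stated effects and at half of them (two-sided, at half: 23% for 6MWT, 60% for SSWS, 38% for FCWS).

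The cost is a few sentences, with no extra patients or visits. Holm costs almost nothing at the stated effects and about 20 percentage points in the chance of at least one success if between-arm effects are half as large. A single lead test avoids that adjustment but rests the conclusion on one measure.

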### ***Secondary outcomes***

The change in strength of brain activity in affected regions of interest (ROI) within the brain, and the change in laterality index (LI) comparing the same ROI in affected and unaffected hemispheres. Regions of interest include the primary sensorimotor cortex, the supplementary motor area, and the cerebellum.

Normative data on the progression of motor learning (behavioral measures) and brain activity (fMRI) in control subjects of similar age to the stroke-prone population (50-85 years).

## **Research Design and Methods**

Forty (40) adult stroke patients as well as 80 healthy controls will be enrolled in this study. The 40 stroke patients will be subdivided into two equal groups; the “robotic” group will receive the targeted training task, while the “control” group will perform duration-matched aerobic pedaling. 20 healthy controls enrolled (age 50-85) will contribute to a normative data set. They will receive up to 5 training sessions in a modified robotic paradigm and up to 1 fMRI scan. The other healthy control subjects (age 18-50) will participate as pilot subjects during early phases while the device and therapeutic task specifications are developed, and throughout the project while the device and tasks are refined. These pilot subjects will test the robotic device; help us determine how subjects are able to control muscle activity and foot endpoint force, independent of neurological injury; and/or test the fMRI scanning protocol and exercises. Because these subjects are contributing to development, we have no a priori expectation of how many will be needed. We guess roughly 20, but we plan to recruit as many as ongoing development needs require (up to 60).

Several studies have shown that recovery of functional and motor capabilities after a stroke is a long process that occurs over several months and even years following a stroke (Takahashi et al., 2005; Ward et al., 2003). Similarly, age is a significant factor that influences recovery. The current protocol is aimed at developing a rehabilitation device and protocol that has the potential to facilitate recovery in patients with lower-limb motor impairments. This is a Pilot study and the results of this study should help us to identify the patients and level of impairment for which this intervention is most optimal. The long-term goal is to apply this therapy to patients at all stages of recovery from stroke. However, we initially restrict ourselves to a subset of patients based on time since stroke onset, to reduce likely statistical scatter in the results. Each patient will serve as their own control in this repeated-measures design (evaluations pre-intervention and post-intervention).

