### **Patients:**

Inclusion criteria:

- Subjects will be stroke patients with persistent moderate unilateral lower extremity deficits, age 50-85 years at time of enrollment.
- Time since stroke will be greater than 6 months (“chronic” stroke survivors).
- Persistent moderate unilateral lower-limb impairment (defined as NIH Stroke Scale – Motor Leg section score of 1-2, to be discussed with the patient verbally during phone screening and assessed by the investigator during the initial

enrollment visit).

- Fluent in spoken and written English

Exclusion criteria:

- Allergy to electrode gel, surgical tape and metals.
- Subjects under treatment for infectious diseases will be excluded from the study.
- Women who are pregnant or planning to become pregnant during the course of the study will be excluded.
- Contraindications for MRI
- Age over 85 years at time of enrollment.

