9. Electromyography (EMG) – is the recording of changes in skin voltage caused by contraction of the underlying muscles. This recording will be obtained using the EMG recording equipment incorporated in the rehabilitation cycle. EMG electrodes will be attached to the surface of the skin over selected muscles of interest in the legs. Muscles may include tibialis anterior, gastrocnemius (medial and lateral), soleus, peroneus longus, peroneus brevis, vastus medialis, vastus lateralis, rectus femoris, iliopsoas, biceps femoris (medial and lateral), semitendinosus, gluteus maximus, gluteus medius, and tensor faciae latae. Proper electrode placement is made according to recommendations from the literature (De Luca, 1997; Rainoldi et al., 2004; SENIAM). A reference electrode will be attached over a bony landmark such as the kneecap, elbow or anterior superior iliac spine (ASIS). Wires will be restrained by tight-fitting clothing, straps or skin-safe tape to prevent motion artifacts. EMG signals will be pre-amplified at the sensor site, and simultaneously recorded by (i) a computer data acquisition system, and (ii) a microcontroller used to control the robotic cycle. Electrodes will be either single-use adhesive electrodes or reusable electrodes. EMG signals will be used as input to the robotic controller as well as for evaluation of outcomes.
10. Leg strength: will be assessed using isometric contractions against the instrumented pedals of the rehabilitation cycle.
11. Health Questionnaire: to document the general physical health and social habits of all subjects.
12. Pain Scale: Patients will be asked to rate their degree of pain on a scale of 0 (no pain) to 5 (in tears).
13. Modified Ashworth Scale: will be used to assess muscle tone in each hip and knee.
14. Fugl Meyer Assessment (FMA): range of motion testing of lower and upper limb capacity. The lower-limb section of the 37-item FMA (11 items) (Hsieh et al., 2007) will be used to categorize stroke severity at the time of block randomization into one group or another. If time allows, the complete 37-item FMA will be performed instead for completeness.

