### **Subject randomization:**

Subjects with stroke will be randomly assigned to the intervention [robotic] or non-intervention [aerobic/control group]. Randomization will be done using a block design. We will control for sex (male vs female) and stroke severity (based on Fugl Meyer assessment) to ensure comparability across groups.

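### Randomisation is balanced on sex and Fugl-Meyer severity, but no planned between-arm analysis includes either factor, and no planned analysis relates response to severity

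*Combined protocol and SAP*

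**What the plan says.** **Purpose.** Research Design and Methods says that "the results of this study should help us to identify the patients and level of impairment for which this intervention is most optimal". The same paragraph adds that "we initially restrict ourselves to a subset of patients based on time since stroke onset". It does not mention the limit on impairment there.

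**Entry.** The patient inclusion criteria require moderate unilateral leg impairment, "defined as NIH Stroke Scale – Motor Leg section score of 1-2", and stroke more than 6 months earlier.

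**Randomisation.** Subject randomization states: "We will control for sex (male vs female) and stroke severity (based on Fugl Meyer assessment) to ensure comparability across groups". Under Behavioral Assessment, the lower-limb section of the Fugl-Meyer "will be used to categorize stroke severity at the time of block randomization into one group or another". No cut-points are given. The battery is given to all patients at the start and the end.

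**Analysis.** Under Behavioral Data, the repeated measures ANOVA has "time as the independent variable and score on" each behavioural test as the dependent variable. The multivariate ANOVA has Time within subject and "Group (robotic therapy, aerobic therapy) as the between-subject factor". The fMRI section adds unpaired t-tests between arms and an ANOVA with Group and Time.

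**The concern.** Balancing on a prognostic factor removes that factor's contribution from the true variability of the arm difference. If the analysis then leaves the factor out, its contribution stays in the residual variance. The estimated standard error is too large, the interval too wide and the test conservative. A trial with 16 planned completers per arm has little precision to give away.

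Separately, the design section expects the results to say something about which level of impairment suits the therapy, and no planned analysis relates response to severity. Without a pre-specified estimate, the question is likely to be taken up by unplanned subgroup comparisons. At this size those are unreliable, yet they could influence whom a later full-scale study recruits.

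**Working it through.** **1. Do sex or severity appear in any planned analysis of the patients?**

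| Planned analysis | Terms | Baseline severity or sex? |
|---|---|---|
| Behavioural repeated measures ANOVA | Time | No |
| Multiple regression | Last-session EMG and foot-force tracking error; fMRI percent signal change | No |
| Multivariate ANOVA | Time, Group | No |
| fMRI unpaired t-tests | Group | No |
| fMRI repeated measures ANOVA | Group, Time | No |

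The Fugl-Meyer score could enter as an outcome, being one of the behavioural tests. It is never a covariate or an effect modifier.

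**2. The plan's own sample size.** Inputs from Sample Size: 6MWT 154.3 m (SD 171.1), SSWS 0.21 m/s (SD 0.13), FCWS 0.18 m/s (SD 0.15); z = 1.96 or 1.65, and 0.84. Formula: n per group = 2((z₁ + z₂) × SD / d)².

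- 6MWT: 2(2.80 × 171.1/154.3)² = 19.28, so 20; one-tailed 15.25, so 16.
- SSWS: 6.009 (stated as 6); one-tailed 4.75, so 5.
- FCWS: 10.89, so 11; one-tailed 8.61, so 9.
- Dropout: 16/(1 − 0.2) = 20 per arm.

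These reproduce, apart from SSWS rounded down by a hair. They address overall differences only; there is no figure for a severity or sex analysis. Below, the stated differences and SDs serve as the planned between-arm effects and SDs, as the plan's formula uses them.

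**3. Cost of omitting the balancing factors.** With balanced arms, the SE is inflated by 1/√(1 − R²), where R² is the share of the variance of *change* explained by sex and Fugl-Meyer. The documents give no R²; 5% to 20% is assumed.

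- R² = 0.05: 1/√0.95 = 1.026, about 3%.
- R² = 0.20: 1/√0.80 = 1.118, about 12%.

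For the 6MWT, the unadjusted SE is 171.1 × √(2/16) = 60.5 m. Adjusted, it would be 60.5 × √0.95 = 59.0 m or 60.5 × √0.80 = 54.1 m. Two-sided power, Φ(154.3/SE − 1.96), is 72% unadjusted, and about 74% or 81% adjusted.

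**4. What a severity analysis could show.** Assume 16 completers per arm, two severity levels and 8 patients per cell (the documents give no split).

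- 6MWT, arm difference within one level: SE = 171.1 × √(2/8) = 85.6 m; 95% half-width 1.96 × 85.6 = about 168 m.
- 6MWT, difference between levels: SE = 171.1 × √(2/8 + 2/8) = 121.0 m; half-width about 237 m.

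Two-sided power for the interaction, Φ(effect/SE − 1.96):

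| Assumed interaction and split | 6MWT | SSWS | FCWS |
|---|---|---|---|
| Equal to the planned effect, 8/8 | 25% | 63% | 40% |
| Half the planned effect, 8/8 | 9% | 21% | 13% |
| Equal to the planned effect, 4/12 | 20% | 51% | 31% |

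A noncentral t calculation gives slightly less in the first row (23%, 60%, 37%). For 80% power at the full-size interaction with an even split, about 78, 25 and 44 per arm would be needed.

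**The case against.** **The stated purpose is soft.** The sentence says the results should help, sits in a design paragraph, and has no counterpart in the Specific Aims, Study Objectives or Study Outcomes. The Specific Aims already limit the study to chronic impairment of moderate severity. This stands: a reader might infer an unmet formal objective, and the documents do not support that.

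**The trial is not silent on impairment.** A reader might infer that it yields no information on severity. That is too strong. Fugl-Meyer is collected from all patients at both time points, so a pattern within the entry range can be described. What is missing is a pre-specified analysis linking it to response.

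**The limit to chronic stroke is disclosed.** The design section states it, gives the reason and treats other stages as a long-term goal. It is not a fault.

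**Each patient is their own control.** Stable differences in walking level due to sex or severity cancel in a pre/post comparison. This stands, and it is why R² above refers to change. If the factors hardly predict change, adjustment gains almost nothing.

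**The 6MWT is the least favourable outcome.** The Sample Size section itself calls it the outlier, so all three gait measures are shown. Low interaction power is normal in a pilot, and pre-specifying the term will not raise it.

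**Conclusion.** The point holds as a cheap improvement to the analysis. It does not show that the trial is invalid. Randomisation uses sex and Fugl-Meyer severity, no between-arm analysis contains either, and nothing planned connects response to severity despite the remark in the design section.

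The omission does not bias the arm comparison; it makes it less precise than it need be. The loss is about 3% to 12% of the standard error, and it rests wholly on the assumed 5% to 20% of the variance of change. The severity figures rest on an assumed split and an assumed interaction size, and a two-level split is itself a simplification of a continuous score. They support exploratory description of effect modification within NIHSS leg scores 1-2. They do not support identifying a best level of impairment, and patients outside that entry range cannot be addressed at all.

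**What to change.** 1. **Behavioral Data and fMRI data sections.** Make the between-arm comparison of each gait and fMRI outcome a linear model of the post-training value (or the change) on Group, adjusted for the baseline value, baseline lower-limb Fugl-Meyer score (continuous) and sex. This replaces the unpaired t-test, which cannot take covariates. If the repeated-measures form is kept, add Fugl-Meyer × Time and sex × Time. Main effects alone would leave the Group × Time test no sharper.

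2. **Effect modification.** Add one exploratory estimate for each gait outcome: Group × Fugl-Meyer in the post-training or change model, or Group × Time × Fugl-Meyer in the repeated-measures model. In the latter, Group × Fugl-Meyer alone describes severity differences averaged over both time points and not differential response. Report it with its confidence interval and no significance claim.

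3. **Research Design and Methods.** Limit the sentence to exploratory description of how response varies with Fugl-Meyer score among chronic patients with NIHSS leg scores 1-2.

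**Cost.** The scores are already collected, so no new visits or patients are needed. The change adds three terms in total (Fugl-Meyer, sex and, in the exploratory model, the interaction), plus the baseline value where that is fitted. With 32 completers, a Group-only model of change has 32 − 2 = 30 residual degrees of freedom, so this is affordable. The other cost is a more modest stated purpose.
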